1.0 Study Summary

Study Title	Technology-based fall risk assessments for older adults in low-income settings
Study Design	We will use a cross-sectional design to address our aims and test hypotheses.
Primary Objective	Examine the associations among fall risk appraisal, body composition, and physical activity.
Secondary Objective(s)	-Examine the feasibility of recruitment (e.g., how many older adults (OAs) need to be screened to recruit the sample?), especially during the COVID-19 pandemic, and acceptability of technologies and procedures for use among OAs in low-income settings. -Determine the dynamic relationships between fall risk appraisal, body composition, physical activity, and behavioral changes related to fear of falling
Research Intervention(s)/ Investigational Agent(s)	NA
IND/IDE #	NA
Study Population	Adults aged 60 years and older
Sample Size	120 participants for timepoint 1 60 participants for timepoint 2
Study Duration for individual participants	Total 9 days with two visits (105-158 mins, total)
Study Specific Abbreviations/ Definitions	Older Adults (OAs) Physical Activity (PA) Fall Risk appraisal (FRA) Fear of Falling (FOF) Assistive Health Technology (AHT) BTrackS Balance Plate (BBP) BTrackS Balance System (BBS) Body Mass Index (BMI) Bioelectrical Impedance Analysis (BIA) Fall-Efficacy Scale International (FES-I) Patient Health Questionnaire-9 (PHQ-9)

2.0 Objectives*

Aim 1. *Examine the feasibility of recruitment (e.g., how many OAs need to be screened to recruit the sample?), especially during the COVID-19 pandemic, and*

acceptability of technologies and procedures for use among OAs in low-income settings.

Aim 2. *Examine the associations among fall risk appraisal, body composition, and physical activity.*

H2.1: Rational FRA is associated with higher levels of PA and skeletal muscle mass, and lower levels of percent of body fat and BMI.

H2.2: Incongruent FRA is associated with higher levels of PA and skeletal muscle mass, and lower levels of percent of body fat and BMI.

H2.3: Irrational and congruent FRAs are associated with lower levels of PA and skeletal muscle mass, and higher levels of percent of body fat and BMI.

Aim 3. Determine the dynamic relationships between fall risk appraisal, body composition, physical activity and behavioral changes related to fear of falling.

3.0 Background*

3.1

[figure not shown]
More than 15 million (30%) OAs in the US have incomes below the 200% of poverty line.^{1, 2} Poverty rate increases with age, and is higher among women, Blacks and Hispanics, and individuals with poor health.¹ OAs who live in low-income communities are less likely to engage in PA,³⁻⁵ defined as any bodily movement produced by skeletal muscle that results in energy expenditure.⁶ Lack of PA is related to chronic conditions and reduced quality of life among low-income OAs.^{7, 8} Limited data suggest that OAs who overestimate their fall risk and report fear of falling (**FOF**) are less likely to participate in PA, and the association between FOF and PA intensity differs by fear severity.⁹ Changes in body composition also have a significant impact on functional capacity and quality of life.¹⁰ However; these studies have not included OAs from low-income settings, who are more likely to report falls in the prior year.¹¹ Recent systematic reviews found that most studies have not used objective measures of fall risk and PA.^{5, 12} We will use objective measures of body composition, balance performance, and PA among OAs from low-income settings.

Additionally, up to 50% of OAs who have FOF limit their daily physical activity (**PA**) because of the fear.¹³ The COVID-19 pandemic is causing increased fear and related to perceived risks for loved ones and health anxiety.¹⁴ Physical distancing and fear of the virus have led to reductions in OAs' use of routine healthcare and performing daily PA.¹⁵ With the high levels fear; individuals may not think rationally when reacting to COVID-19 and taking care of themselves.¹⁶

3.2

One-third of OAs have maladaptive **fall risk appraisal**

(FRA), a condition in which there is a discrepancy between perceived fall risk (levels of FOF) and physiological fall risk (balance performance).^{17, 18} Measuring FRA in OAs can be challenging due to self-report bias and cognitive deficit.^{19, 20} Using both subjective and objective measures provides better fall risk assessment among OAs.^{20, 21} Thus, we developed a *fall risk appraisal matrix*, a graphical grid categorizing levels of FOF and balance performance into four quadrants (Fig 1): **1) rational FRA** (low FOF and normal balance), **2) incongruent FRA** (low FOF despite poor balance), **3) irrational FRA** (high FOF despite normal balance), and **4) congruent FRA** (high FOF and poor balance).¹⁷ In our pilot study (N=102), we measured FOF by a questionnaire and balance performance using a portable and novel force balance plate (BTrackS Balance System; **BBS**). We found that 40% of OAs had maladaptive FRA. Of this group, 19% with incongruent FRA and 30% with irrational FRA reported falling in the past year.¹⁷ OAs with congruent FRA were 3.29 times more likely to fall than those with rational FRA.²² However; our sample included only 11% of low-income OAs.

3.3

Maladaptive FRA may impede low-income OAs participation in PA and can result in social isolation.^{20, 23} Irrational FRA serves as a barrier, creating an irrational fear that inhibits OAs from staying active. Conversely, incongruent FRA can act as an impediment to OAs' safety by fabricating a sense of wellbeing when more caution is warranted. Rational FRA is a crucial component of regular engagement in PA.²⁴ However, research has not examined the association between FRA and PA among low-income OAs. We will examine the association between FRA and PA among low-income OAs.

Body composition (e.g., obesity, low relative skeletal muscle mass) has been associated with FOF, functional impairment, and disability in American OAs.²⁵⁻²⁷ Higher BMI and percent body fat were associated with poor physical function while percent appendicular lean mass was associated with better physical function (e.g., walking, balance test).²⁶ OAs who have higher daily PA have better physical function than those who engage in less PA.²⁸ Although Body Mass Index (**BMI**) is the most widely used measurement to classify overweight/obesity status. It is prone to measurement error and does not consider body fat distribution and skeletal muscle mass.²⁹ We will use the Bioelectrical Impedance Analysis (**BIA**) device, which measures body composition and has established normative data among OAs.³⁰

Research has not examined the associations among body composition, FRA, and PA using Assistive Health Technology (**AHT**), which is the application of organization knowledge, skills, procedures, and systems in order to improve functioning.³¹ Majority of studies have used self-reported measures of fall risk and PA among OAs.³²⁻³⁶ OAs who overestimate their fall risk are less likely to participate in PA.^{24, 37} AHT eliminates recall bias associated with subjective

measures.^{38, 39} Systematic reviews also indicate the importance of technology-based assessments for PA and prevent falls.^{40, 41} We will examine the associations among body composition, FRA, and PA using AHT, including the Bioelectrical Impedance Analysis⁴², BTrackS Balance System,^{43, 44} and accelerometer-based physical activity devices. These devices are portable, non-invasive, safe, valid, reliable, and allow for home testing.^{26, 30, 45, 46}

4.0 Study Endpoints*

4.1

We expect to complete data collection within two years. The study will conclude after the study results are published (~10 years, October 30, 2031).

5.0 Study Intervention/Investigational Agent NA

6.0 Procedures Involved*

6.1 Describe and explain the study design.

We will use a cross-sectional design to address our aims and test hypotheses. Using novel technologies to advance fall risk assessments is one of the essential recommendations for promoting PA.^{47, 48 17, 37, 41, 49} To accomplish this goal, we employ the behavioral epidemiology framework⁵⁰ to understand

the associations among body composition, FRA, and PA.

This framework consists of 5 phases: (1)

establish links between behaviors and health, (2) develop measures of the behaviors, (3) identify influences on the behaviors, (4) evaluate interventions to change the behavior, and (5) translate research into practice.⁵⁰ We focus on Phase 1 and in our model, body composition is an antecedent of FRA and the accelerometer-based PA is a consequence of FRA. We consider OAs' characteristics (e.g., sex) as covariates and control for them in the analysis (Fig 2).

[figure not shown]

Fig. 2 Conceptual Framework

6.2 Provide a description of all research procedures

We will administer the study instruments which consist of objective and subjective measures (see Table 1) for total 120 participants. Participants will complete questionnaires about OA's characteristics, socio-demographic, medical history, cognition, depressive symptoms, anxiety,

and FOF. We will also assess static balance performance using the BTrackS Balance System^{43, 44}, assess dynamic balance using a sit to stand test, assess body composition using the Bioelectrical Impedance Analysis device⁴², and assess handgrip strength test using a hand-grip dynamometer (JAMAR 5030J1). They will wear an accelerometer-based physical activity device for 7 consecutive days.

Table 1. Description of study variables and instruments

Variable	Instrument	Description
OA's Characteristics - Socio-demographics and medical history -Cognition - Depressive symptoms -Anxiety and day-to-day experiences	Self-report questionnaire - Memory Impairment Screen (MIS) ⁵¹⁻⁵³ -Patient Health Questionnaire-9 (PHQ-9) ^{54, 55} -Geriatric Anxiety Inventory-Short form (GAI-SF). ⁵⁶⁻⁵⁸	e.g., age, gender, living status, education level, socioeconomic status, perceived general health, comorbidities, FOF, frailty, fall risk, and social network. - The Memory Impairment Screen (MIS) is a widely used test of cognitive function and screening Alzheimer's disease among OAs. It is a 4-minute, four-item delayed free and cued recall memory test with controlled learning and high discriminative validity. The maximum score for the MIS is 8 and if score 5-8=no cognitive impairment and score ≤ 4 =possible cognitive impairment. -10 items (e.g., feeling tired) on a 4-point scale; measures symptoms of depression within the prior 2 weeks; Total scores range 0-27, scores ≥ 10 moderate depression. ⁵⁴ Cronbach's alpha=0.89 among OAs. ^{54, 55} - The GAI-SF is an abbreviated version of GAI comprising only five of the original items. The GAI-SF has good internal consistency, convergent and divergent validity, and was highly

	
- Trait Mindful Attention Awareness Scale (MAAS).⁵⁹
	
correlated with the original GAI.^{57, 60} A score of three or greater was optimal for the detection of DSM-IV Generalized Anxiety Disorder (GAD) in community-dwelling OAs (sensitivity 75%, specificity 87%). Internal consistency was high (Cronbach's $\alpha = 0.81$) and concurrent validity against the State-Trait Anxiety Inventory was good ($r_s = 0.48$, $p < 0.001$).⁵⁷
 
Day-to-day experiences will be assessed by the trait Mindful Attention Awareness Scale (MAAS). The MASS is a 15-item scale with English and Spanish versions. The MMAS has been validated for use with community adults and has demonstrated high reliability and validity.⁵⁹

Fear of falling (FOF), ageing perceptions, behavioral avoidance/inhibition, and regulatory focus. (Please see Appendix E)
	
Short Fall Efficacy Scale International (Short FES-I)⁶¹
 
-Brief Ageing Perceptions Questionnaire
	
7-items (e.g., going in or out of a chair) on a 4-point scale; measures concerns about the possibility of falling when performing seven activities (e.g., getting dressed).⁶² Total scores range 7-28.⁶¹ Higher total scores=higher FOF.⁶³ Scores 7-10=low concern about falling; scores 11-28=high concern about falling.^{62, 64} The short FES-I has been validated in community-dwelling OAs.⁶² Cronbach's $\alpha = 0.97$ and ICC=0.979 among OAs.⁶⁵
 
- Brief Ageing Perceptions Questionnaire (B-APQ) is a multi-dimensional measure of aging perception which consists of 17 items (5 response choices).

	
-Behavioral avoidance/inhibition scales
 
-Regulatory focus Questionnaire (RFQ)
 
-A single fear of falling scale
	
It has good construct validity and internal consistency. Cronbach's alpha =0.75-0.84.⁶⁶
 
-Behavioral avoidance/inhibition scales consist of 24 items with 4 domains and 4 response choices. Cronbach's alpha =0.66-0.76.⁶⁷
 
-Regulatory focus Questionnaire (RFQ) includes two domains including promotion on hopes and accomplishments and prevention on safety and responsibilities. The RFQ consists of 11 items with scores ranging from 1 to 5.⁶⁸
 
-Are you afraid of falling (Y/N) -If yes, did your fear of falling lead you to restrict some of your activities (Y/N).

Static balance performance	BTrackS Balance System (BBS) ^{43, 44}	See description in 6.3
Hand-grip strength test	A hand-grip dynamometer (JAMAR 5030J1)	Hand-grip strength will be measured in kilograms (kg) as maximal isometric force achieved on a hand-grip dynamometer (ICC3,1 = 0.959, SEM = 3.1 kg).
Dynamic balance	Sit to stand test ^{69, 70}	A sit to stand test has been widely used to assess balance and predict falls, and was reliable and validated in community-dwelling OAs. ^{69, 70}
Body composition	Bioelectrical impedance analysis (BIA): InBody S10.	See description in 6.3
Physical activity	ActiGraph GT9X Link wireless activity monitors (ActiGraph LLC.) ⁷¹	See description in 6.3

Physical activity	Rapid Assessment of Physical Activity (RAPA)	9-items related to how physically active in aerobic activity level and anaerobic activity level in the last 4 weeks (Y/N).
Acceptability of technology	-Evaluation form -Short Version of Senior Technology Acceptance	-OAs evaluation of the devices and procedures. -14-items of 4 components, including attitudinal beliefs, control beliefs, gerotechnology anxiety and health conditions (rating from 1-10).

Balance performance will be assessed by the BTrackS Balance System (**BBS**).^{43, 44} BBS includes the portable BTrackS Balance Plate (BBP), and BTrackS Assess Balance Software running on a computer device (Fig 3).

Fig. 3 BTrackS Balance

The BBP dimensions are 15.5" x 23.5" x 2.5", weight 14.5 lbs., and operated on Windows 7 or higher via a USB port. The BBS is manufactured (by the Balance Tracking Systems, Inc.) in California in an FDA Qualified Facility that has achieved ISO 13485 Compliance. The FDA Registration is under Part 890 – Physical Medical Devices and is further categorized within 890.1575 as a Force-Measuring Platform. The FDA Registration number is 3010668481, and the CFDB License Number is 73881.

During the test, a piece of sturdy furniture or a standard walker will be placed within the participant's reach to reduce the risk that FOF will contaminate performance and enable even frail people to participate.⁷² In comparison to the age group, the software utilizes the BBS Normative Database to compare the individual to others in their age group. BBS score is dependent on age and sex but not body size so that the percentile rankings can be determined across various age groups, and for men and women separately.⁷³ A scale from 0 to 100 represents the percentile ranking of the BBS. Score 0-30 indicates low fall risk (normal balance) and ≥ 31 moderate-high fall risk (poor balance).⁷³ BBS has excellent validity using Pearson correlations ($r > .90$) and high test-retest reliability [intra-class correlation coefficients (ICC)=0.83].⁴⁵

This test consists of four, 20 seconds trials. For each trial, the participants will stand as still as possible on the BBP with hands on their hips, and eye closed. This test consists of four trials. This test will take about 5-10 minutes (Please see Appendix F for static balance performance test (BTracks Balance System)).

Body composition will be assessed using a bioelectrical impedance analysis (**BIA**): InBody S10. The BIA is a widely used commercial device that is FDA approved. The BIA is manufactured by the Biospace Corporation Limited, Naples, FL. The BIA InBody S10 uses 30 impedance measurements, 6 frequencies at each of the 5 segments (Right Arm, Left Arm, Trunk, Right Leg, Left Leg). The BIA InBody S10 specification: Frequencies: 1, 5, 50, 250, 500, 1000 kHz, Weight Range 22-551 lbs, Age Range 3-99 years, Height Range 3 ft 1.4 in-7 ft 2.6 inch, Equipment Weight 4.4 lbs, and Dimensions 12.7 x 8 x 46.5 (L x W x H) inches with stand

Fig. 4 BIA InBody S10

and Dimensions 8 x 2.1 x 12.7 (L x W x H) inches without stand. The BIA InBody S10 measures fat mass, muscle mass and body water levels. There are no risks, no dunking, no pinching, no discomfort associated with the use of bioelectrical impedance analysis. Test duration is 1-2 minutes. Reliability of the test-retest of the BIA was high with an ICC of 0.89.⁷⁴

Fig. 5 ActiGraph GT9X

Physical Activity (PA) will be measured by activity monitoring devices. All OAs will wear the ActiGraph GT9X Link wireless activity monitor (ActiGraph LLC.), a tri-axial accelerometer, on the non-dominant wrist for 7 consecutive days. The GT9X Link has a sample rate of 30-100 Hz, a dynamic range of $\pm 8G$, 14 days battery life (rechargeable), 180 days/4 GB data storage, and is water-resistant. Data are collected in 1-minute intervals. A sensor determines whether the device is on or off the wrist. The GT9X Link provides objective 24-hour physical activity measures, including steps, energy expenditure, intensity, and participant's position. Accelerometry is a reliable method of assessing free-living physical activity (ICC=0.98)⁷⁵ and has been validated against direct observation, energy expenditure, and sedentary behavior.^{76, 77} ActiGraph accelerometers have been used for data collection in the National Health and Nutrition Examination (NHANE) surveys and are the most commonly used device in research studies.⁷¹ The device display screen can be disabled, so the device does not display the participant's activity (it will show date and time only).

6.3

We will follow the UCF COVID-19 Human Subject Research (HSR) Standard Safety Plan below:

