If he/she indicates that she/he is ready and wants to participate in this research study, she/he will be asked to complete the questionnaires such as socio-demographics and fear of falling.

Procedure for contacting participants for timepoint 2:

Experimental procedures for both groups

We will assess the static balance performance using the BBS. Participants will take off their shoes and stand as still as possible on the balance plate with hands on their hips and eyes closed for 2-3 minutes. Participants will then complete the

dynamic balance performance test using the sit to stand by full standing up from a chair as many as possible within 30 seconds.

Participants will be stratified by the FRA matrix.¹⁷ We will continually evaluate across four groups (rational/ incongruent/ irrational/ congruent) to maintain equal cell distribution (30 OAs/group)*.

- 1) rational FRA: low FOF [Short Fall Efficacy Scale International (short FES-I) score ≤ 10] and aligned with normal balance (BBS score = 0-30).
- 2) incongruent FRA: low FOF (short FES-1 score ≤ 10) despite poor balance (BBS score= 31-100).
- 3) irrational FRA: high FOF (short FES-I score > 10) whereas normal balance (BBS score= 0-30).
- 4) congruent FRA: high FOF(short FES-I score > 10) and poor balance (BBS score= 31-100).¹⁷

**Please note: This is not an intervention study and subjects will not be assigned to the study group.*

They will perform the hand-grip strength and sit to stand tests. Hand-grip strength will be measured in kilograms (kg) as maximal isometric force achieved on a hand-grip dynamometer. This test will be administered with participants sitting in a chair with feet flat on the floor and the elbow bent at 90°. The dynamometer will be placed in the hand and adjusted so the palm side of the grip will be at the palm, and the front end will be lined up between the joints of the medial and distal phalanges. The grip size will be adjusted so that the second metacarpals were flat with a 90° bend at the knuckles. Participants will be asked to squeeze the strength gauge as hard as possible for 3–5 seconds. Three trials on each hand will be performed with 30-s of rest given between trials. Participants will complete the sit to stand by full standing up from a chair as many as possible within 30 seconds.⁷⁸

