Aim 2 hypotheses are: **1)** Rational FRA is associated with higher levels of PA and skeletal muscle mass, and lower levels of percent of body fat and BMI, **2)** Incongruent FRA is associated with higher levels of PA and skeletal muscle mass, and lower levels of percent of body fat and BMI, **3)** Irrational and congruent FRAs are associated with lower levels of PA and skeletal muscle mass, and higher levels of percent of body fat and BMI. General summary statistics will be presented for continuous data, and percentages will be presented for categorical data. Participant demographic data will be summarized. Analyses will be performed without adjusting for any covariates, followed by the analyses adjusted for age, comorbidities, depressive symptoms, and fall history. Age, the number of comorbidities and the number of falls in the past year will be selected as covariates in the selected model because of their association with FRA, body composition, and PA. Data from InBody770 (e.g., BMI) and ActiGraph (e.g., steps/day) could be modeled as continuous.

Regression models or one-way ANOVA will be used to examine differences in continuous variables (e.g., BMI, steps/day) across the four groups (rational, incongruent, irrational, and congruent FRAs), and categorical variables (e.g., comorbidities) will be tested using Chi-Squared tests. Rational FRA group will set as a base group, and the other three groups (incongruent, irrational, and congruent FRAs) will be compared with this base group. Whenever feasible, models will be adjusted for age, sex, day order, wear time (minutes/day), and the number of fall history. These following variables will add one by one to evaluate the role of each: mobility problems (Y/N), depression (score or category), fall risk (high/low), perceived general health (score of category), medication use (Y/N), and comorbidities (Y/N). A final model will include all significant potential variables to evaluate whether associations between FRA, body composition and PA, whenever feasible.

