Specific Aim 2 Sample Size and Power Analysis. There is no historical precedent and limited information to inform the sample size for this study; therefore, the sample size estimate was based on the variable of the BBS score in our pilot study. The standard deviations of the mean BBS scores in our pilot study were 7.91 in the high PA group and 7.78 in the low PA group (PA by self-report), assuming a two-tail alpha 0.05 and a power 0.8, the estimated total sample size N=120 would allow to sufficiently detect a mean difference about 5 between the two groups. Furthermore, to be able to compare the effect sizes of the different body composition and PA measures, we will perform post-hoc analyses to compare the mean values between the two groups of PA, adjusted for the age group.

Aim 3. Determine the dynamic relationships between fall risk appraisal, body composition, physical activity and behavioral changes related to fear of falling

We hypothesize that higher percentage body fat, and lower frequency and duration of physical activity are associated with fall risk appraisal and the associations vary between four groups. We will collect data at the 2nd timepoint and then a dynamic prediction model will be used to investigate their temporal, dynamic associations.

17.2

We will maintain a master list that will contain identifiable data and links the subject ID codes with the participant's information. The electronic version of this master list will be encrypted, password protected, and stored on a computer and is located in a restricted access room at the College of Nursing. The master list is the only document with identifiable data.

All research data, including identifiers and linking sheets, will be retained for at least 5 years after the study closure.

The de-identified data (such as balance performance test data will be password protected, encrypted, and stored on computers and external hard drives in the restricted access laboratory). The de-identified data will be kept indefinitely. The reason for keeping the de-identified data indefinitely is for scientific reproducibility and transparency.

17.3 NA

17.4

Efforts will be made to limit the use and disclosure of participants' personal information, including research study to people who have a need to review this information. We cannot promise complete secrecy.

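### The BBS cut-off that forms the FRA groups is written on a 0–100 percentile scale that the pilot BBS SDs do not fit, so the plan must say which BBS output it uses

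*Combined protocol and SAP*

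**What the plan says.** Three places in the combined protocol and SAP bear on this.

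- **Section 6.2 (balance performance).** The software compares each person with a normative database. The BBS score is said to vary with age and sex, so that "the percentile rankings can be determined across various age groups, and for men and women separately". Then: "A scale from 0 to 100 represents the percentile ranking of the BBS". The cut-off follows at once: "Score 0-30 indicates low fall risk (normal balance) and ≥ 31 moderate-high fall risk (poor balance".
- **Section 6.4 (experimental procedures).** The FRA matrix uses the same cut-off. Rational FRA is low fear of falling "aligned with normal balance (BBS score = 0-30"; incongruent FRA is low fear "despite poor balance (BBS score= 31-100". Irrational and congruent FRA use the same two BBS ranges. Recruitment is to be watched so that each cell reaches 30.
- **Section 17.1 (Aim 2 sample size).** The basis is the pilot BBS score. The SDs of the mean "BBS scores in our pilot study were 7.91 in the high PA group and 7.78 in the low PA group", and N=120 is said to detect a difference of about 5. No unit is given.

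In the Aim 2 analysis the four groups form the comparison factor: "Rational FRA group will set as a base group".

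**The concern.** A percentile normed by age and sex is built to remove dependence on age and sex. A score that does depend on them is a different quantity, so Section 6.2 describes two BBS outputs. The cut-off comes directly after the percentile sentence, and the upper limit of 100 in Section 6.4 is the top of the percentile scale. Staff who follow the text would probably classify on the percentile. The pilot SDs, however, are far smaller than percentiles normally show.

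At stake is the four-level factor in the main Aim 2 comparisons and the 30-per-cell quota. The choice of scale decides who moves between rational and incongruent, and between irrational and congruent. It also decides whether age and sex are already built into the groups before the models adjust for them. The plan never says whether a high percentile means better or worse balance; only the cut-off implies that higher is worse.

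**Working it through.** **1. The plan's own figure.** Inputs from Section 17.1: SDs 7.91 and 7.78, two-sided alpha 0.05, power 0.80, difference 5. I assume equal physical activity groups.

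- Pooled SD = √[(7.91² + 7.78²)/2] = √61.55 = 7.845.
- n per group = 2 × (1.960 + 0.842)² × 61.55 / 5² = 38.7, so 39 per group and 78 in total.
- At 60 per group the detectable difference is 2.802 × 7.845 × √(2/60) = 4.01, and power for 5 is 93.7%.

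The stated N=120 is not reproduced but is more than enough. This is a separate matter and does not identify the scale, because SD and difference are on the same scale whatever it is.

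**2. Expected SD of a percentile.** If participants resemble their age and sex norms, percentiles are uniform on 0–100 and SD = 100/√12 = 28.87. The ratio to the pilot is 28.87/7.845 = 3.7. The pilot SDs are within activity groups, but that explains little: adding an assumed between-group difference of 5 gives √(61.55 + 2.5²) = 8.23, still a ratio of 3.5.

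**3. Could they be standard errors?** Section 17.1 speaks of SDs of mean scores. With an assumed 51 per group (half of the 102 in Section 3.2), the SD would be 7.845 × √51 = 56.0, above the maximum of about 50 on a 0–100 scale.

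**4. What sample would give a percentile SD of 7.845?** Let percentile = 100·Φ(Z), with Z normal with mean μ and SD s, where s = 1 is the norm spread.

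| Condition | Required s | Mean percentile | Share ≥31 |
|---|---|---|---|
| Norm spread, bunched low | 1 | 3.5 | 2% |
| Norm spread, bunched high | 1 | 96.5 | 99.9% |
| 8% at or above 31 | 0.30 | 18.6 | 8% |
| Centred on the cut-off | 0.23 | 30.9 | 50% |

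Section 3.2 reports 40% maladaptive FRA in 102 people, with fallers in both the incongruent and irrational groups. If its 19% is a share of all maladaptive people, incongruent fallers number about 0.19 × 0.40 × 102 ≈ 8, or 8% of the pilot. If it is a share of the incongruent group, the smallest group that rounds to 19% is 16 (3/16 = 18.75%). Either way at least about 8% had poor balance, so low bunching at norm spread (2%) does not fit. High bunching leaves almost nobody for the irrational group. What remains is a spread of 0.30 of the norm or less. This assumes that Sections 3.2 and 17.1 describe the same pilot and that it used the 30/31 cut-off.

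**5. Illustration of the quota.** Equal cells need 30 + 30 = 60 people at 0–30. Uniform percentiles give 0.30 × 120 = 36, with about 70% labelled as poor balance by construction. If the sample mean lies 0.5 norm SD on the poor-balance side, the count is about 19. At 0.5 and 1 SD on the good-balance side it is about 60 and 83.

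**The case against.** The best defence is that the rule may already refer to the unranked score. Section 6.2 separates the score from the rankings derived from it, the cut-off sentence speaks of a score, and Section 6.4 says BBS score. On that view only the limit of 100 is loose wording. This is a fair reading, but the text does not settle it: the cut-off sits right after the percentile sentence and no other unit is offered.

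Secondly, 28.87 holds only for a sample resembling the norms, and a bounded percentile can have an SD near 7.9. That stands as a matter of logic. The SD mismatch is strong indirect evidence, not proof.

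Thirdly, the cut-off may truly belong to the percentile, with only the Section 17.1 SDs on another scale. Classification would then be sound and only the sample-size basis would need relabelling. The documents do not exclude this.

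A reader might also set the planned difference of 5 against an SD of 28.87 and conclude that the study is badly underpowered. That does not follow. If the SDs are on an unranked score, so presumably is the 5, and the calculation would mix two scales. It also compares physical activity groups, not FRA groups.

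**Conclusion.** The concern holds as an unresolved inconsistency. What the figures make implausible is that the cut-off and the pilot SDs are both on the percentile. That leaves two readings:

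- The cut-off and the SDs are both on the unranked score. The percentile wording in Sections 6.2 and 6.4 is then wrong, and following it could misclassify participants.
- The cut-off is on the percentile and the SDs are not. The groups are then as intended, and Section 17.1 needs correction.

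A reader might infer that the groups will be misclassified, or that the unranked score is the right one. The documents support neither: they give no unranked unit, no pilot mean and no statement of which output the cut-off was derived on. The number misclassified cannot be computed. The 36 of 120 is an illustration that rests on uniform percentiles, and the true figure depends on the sample.

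Nor is FRA group the exposure in every analysis. Section 6.1 treats body composition as an antecedent of FRA, and Section 17.1 plans post-hoc comparisons between physical activity groups. It is, however, the factor in the main Aim 2 comparisons and the basis of the quota, so its definition needs to be reproducible.

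**What to change.** Check the pilot scoring file to establish which BBS output the 30/31 cut-off was applied to and on which scale 7.91 and 7.78 were measured. Do not presume the answer. Then reconcile Sections 6.2, 6.4 and 17.1:

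1. Name one BBS output for the rule, with its unit and the direction that means worse balance, and classify FRA only on that output.
2. Remove the wording that belongs to the other scale. If the cut-off is on the unranked score, that is the 0–100 percentile wording and the upper limit of 100.
3. In Section 17.1, state the scale of the pilot SDs and of the difference of 5.

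The cost is a file check and a wording change, with no new data collection. If anyone has already been classified, confirm which output was used for them.
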